7.1 Household-level questionnaire

A household will be defined as any single permanent or semi-permanent dwelling structure acting as the primary residence for a person or group of people that generally cook and eat together. Some households may include members who sleep in other dwelling structures within the same compound, if the members are still dependent on the head of household in the main household. A household resident will be defined as any person who has spent at least one night in the household in the past 5 weeks.

For each household enrolled in the study, a brief questionnaire will be conducted with the acting household head. The purpose of this questionnaire will be to determine household size and obtain information about the household structure as well as coverage of vector control interventions. If certain individuals are not present, the questionnaire will also aim to schedule a more suitable time to reach absent individuals. Separate questionnaires will be used for the RACD and TPE arms. The RACD household level questionnaire will collect blood testing results. The TPE questionnaire will collect information about doses of drugs administered (Appendix K).

7.2 RACD arm - Perform RDT and refer secondary cases to health facilities

Individuals residing in RACD clusters will be tested by RDT using the *Pf*-specific First Response RDT during the intervention visit. At the time that blood is collected for RDT testing, the same finger prick will be used to generate a slide and dried blood spot. Four spots of blood will be collected for each DBS. Subjects testing positive by RDT will be referred to the closest health facility for treatment according to national policy (first line AL, second line Oral quinine for uncomplicated malaria).

Secondary cases detected by RDT will become index cases (using the same unique study ID) and receive a case investigation. For these secondary cases, a second finger prick will also be performed to collect 250uL blood in a microtainer. These secondary cases will also be invited to participate in the 6-9 months follow-up as well as the end-line survey at the end of the study (expected mid 2017).

The microtainer samples collected from secondary cases will be used to develop serologic and genotyping methods. The rationale for a larger volume of blood is that serum is the gold standard sample for serologic assessment. Although DBS collection is more practical and has been validated for use in population level serologic assessments (as will be done at the end-line survey at the end of the study, expected mid 2017) [19], this microtainer sample will be used to develop and validate our serologic assay. A larger volume of blood draw will also facilitate genotyping. Secondary cases are mainly asymptomatic individuals with low-density infections. In our experience, microsatellites do not usually amplify well when using DBS in asymptomatics.

7.3 TPE arm - Administration of DP

Individuals enrolled in the TPE arm will be interviewed to determine if it is safe for them to receive DP (Eurartesim, Sigma Tau).

For individuals who can safely be given DP, the dose is one daily dose for 3 consecutive days. Participants will be weighed at enrollment, and DP will be dosed according to weight-based guidelines (Appendix Q). Half-strength DP tablets (20/160mg) or full strength DP tablets (40/320 mg) that have been cut into half will be given to children weighing ≤ 12 kg, and full-strength tablets (40/320mg) will be given to those weighing >12 kg.

The first DP dose will be administered by DOT. Subsequent doses will be left with the subject or guardian and subjects will be instructed to self-administer at the same time on Days 2 and 3. If a dose is missed, it should be taken as soon as realized and then the recommended regimen continued until the full course of treatment has been completed. No more than one dose on the same day should be taken to make up for any missed dose. Study staff will be revisiting neighborhoods for up to 2 additional days to enroll more subjects. On those days, the study staff may remind subjects.

The drug insert suggests that DP should be taken orally with water and without food, the concern being that food may increase absorption of piperazine. However, there is limited data to support this practice. A trial by Lwin et al. in Thailand compared DP ingestion with or without chocolate milk and found both approaches to be safe, with no difference in drug levels or efficacy. [20] Several trials from Africa using DP in symptomatic as well as asymptomatic individuals have not required administration without food and have not found safety risks.[11-15, 21]. Given the limited data to show adverse events with food administration, and the practical challenges of administering DP without food in the field, we will not impose this restriction.

The shelf life of DP is 24 months. Expired drugs will not be used. As recommended, DP will not be stored above 30°C.

If an individual cannot safely be given DP, that individual will not be given medication for presumptive treatment. Pregnant women and breastfeeding women will be excluded. All girls ≥ 10 years of age will also be asked about menses. Those who have had menarche but have not menstruated in the past 4 weeks will also be excluded. Infants < 9 months of age or < 7 kg will also be excluded. For infants and children unable to take tablets, drugs will be crushed, mixed with water and administered as a suspension. No more than two courses of DP may be given within a 12-month period. Additionally, a second course of DP should not be given within 2 months after the first course due to the long elimination half-life of piperazine. Other contraindications include: severe malaria, young children who vomit (electrolyte disturbances can increase QTc), heart problems or rhythm disturbances, kidney or hepatic insufficiency, recent treatment with certain medications (antiarrhythmics, neuroleptics, antibiotics, non-sedating antihistamines, antimalarial agents, and others (cisapride, droperidol, domperidone, bepridil, dephemanil, probucol, levomethadyl, methadone, vinca alkaloids, and arsenic trioxide).

Individuals who cannot safely be given DP will be tested by RDT using the *Pf*-specific First Response RDT during the intervention visit. At the time that blood is collected for RDT testing, the same finger prick will be used to generate a slide and dried blood spot. Four spots of blood will be collected for each DBS. A second finger prick will be used to collect microtainer blood samples from RDT-positive individuals. Subjects testing positive by RDT will be referred to the closest health facility for treatment with a drug that is safe for them according to national policy.

7.4 Management of sick participants

During the intervention, individuals who have a temperature of $\geq 38.0^\circ\text{C}$, report having a fever in the past 48 hours, or have other illness will be referred to the nearest health facility for further evaluation.

7.5 Adherence assessment

In order to evaluate adherence to DP via modified DOT in the TPE arm, study staff may return in 7-10 days to perform a pill count. There is limited data on the expected adherence to the 3 day regimen among asymptomatic individuals. Among symptomatic individuals, the reported adherence ranges from 39 to 100%. [22] Due to the return visits by study staff, engagement of rural health motivators, and perceived risk among individuals residing near an index case, we hypothesize that adherence to a 3 day regimen will be 80%.

[figure not shown]

Figure 7. Study procedures.

8 Adverse event monitoring

8.1 Overview

The safety risks associated with participation in this trial are expected to be minimal. AL, the current standard of care in Swaziland, is generally well tolerated and, at least by passive monitoring, has been associated with only minimal adverse effects in Swaziland. DP is one of the ACT regimens recommended by the WHO[23], and is recommended as a second line treatment for uncomplicated malaria in many countries[24]. The safety and tolerability of DP have been closely evaluated in clinical trials evaluating DP for treatment and prevention of malaria, and DP has been shown to have an excellent safety profile[10, 11, 25, 26]. In the TPE arm, prior to drug administration, subjects will be asked about known allergy, past adverse reactions felt to be associated with treatment, and other contraindications (see Table 3) and will be excluded from taking drug if such a history is reported.

Adverse event monitoring of SAEs potentially related to AL or DP will occur passively. Subjects will be instructed to seek care at their local health facility if they experience any serious adverse reactions that may be related to AL or DP. Health facility physicians will determine if a participant should continue or stop treatment due to safety concerns. Health facility staff will be asked to notify study staff of all adverse events. For any adverse events that are reported in either arm, we will attempt to assess causality by collecting additional data on the relationship between the drug and the event. This information will be reported and reviewed by the Pharmacovigilance and Adverse Drug Reactions Committee (the Data Safety & Monitoring Board for this study).

8.2 Definitions

- Serious adverse event (SAE): An experience that results in (1) death during the study period; (2) life-threatening experience (one that puts a participant at immediate risk of death at the time of the event); (3) inpatient hospitalization during the study period; (4) persistent or significant disability or incapacity, (4) specific medical or surgical intervention to prevent one of the other serious outcomes listed above.
- Suspected Unexpected Serious Adverse Reactions (SUSAR): An adverse drug reaction that is suspected of having a causal relationship to the trial medication and is unexpected

8.3 Passive identification of SAEs

Participants will be instructed to seek care at the nearest health facility if they develop a serious illness (see Appendices E & F). Also, the national emergency '977 Hotline' can be used to allow participants to receive care for urgent medical conditions. Health facility physicians, in consultation with the study physician, will decide if a participant should continue or stop treatment due to safety concerns. For less serious symptoms, participants should contact the attending study nurse to advise and quickly attend to the participant's needs. Study personnel will assist with referrals as needed. Participants will be instructed to notify their attending Study Nurse with any adverse events that may be related to either AL or DP. Health facilities will also be notified about the study and asked to call the attending Study Nurse who will be available by telephone 24 hours/day, 7 days/week.

For any potential serious adverse events that are reported in either arm, the study team will arrange follow-up visits within 24 hours at a convenient location (at home, school, or a health care facility) to complete an SAE form. This information will be reported to and reviewed by the Pharmacovigilance and Adverse Drug Reactions Committee.

8.4 SAE report forms

For each serious illness identified, an adverse event report form will be completed (Appendix S). The following information will be recorded for all experiences that are reported:

- Description of the subject (ID number, age, gender, weight)
- Name of the event
- Description of the event and management of illness
- SAE criteria met
- Date of event onset, date of resolution, and date event reported
- Maximum severity (Appendix T)
- Causality and expectedness
- Drug history (names, doses, dates administered for all drugs taken one month prior)
- Past medical history, including known allergies
- Management and outcome of the event

8.5 Expedited reporting of SAEs and SUSARs

All reports of serious adverse events that are classified as at least ‘possibly’ related to administration of study drugs, including those classified as possibly, probably, or definitely related, and reports of all suspected & unexpected serious adverse reactions will be entered into a database and a listing of these events will be submitted to the IRBs, the Pharmacovigilance and Adverse Drug Reactions Committee, and the drug manufacturer according to their guidelines for expedited reporting.

8.6 Management of participants with SAEs

If a study participant experiences a SAE classified as related to a study drug, decisions on whether the participant should complete treatment or stop will be made by the health facility worker providing treatment at the health center. Health facility workers may consult with the Study Nurse or the Study Physician. Factors that will be considered will include the type and severity of the event, and suspected strength of the association between drug and the event (possibly, probably, or definitely related). In all cases, the potential risks and benefits will be weighed, and decisions will be guided by the best interest of the patient. The Study Physician will investigate to assess associations and severity, and will follow up with cases to ensure resolution. The Study Physician may consult with his or physician colleagues to review associations and severity.

9 Follow-up surveys

9.1 Overview

Prior to implementing the intervention in each Target Area, a baseline blood survey will only be conducted in the RACD arm. Blood testing will not be performed pre-intervention in the TPE arms as the trial was designed to be operationally relevant so that feasibility (coverage, acceptability, etc.) could be assessed. In both the TPE and RACD arms, a follow-up blood survey will be conducted toward the end of the study during the end-line survey, expected to take place mid 2017. In index and secondary cases and a subset of RDT-negative control subjects from the RACD arm, a follow-up survey will also be conducted at 6-9 months for serological assessment. Finally, using routine health facility data from blood draws in symptomatic individuals, incidence data will be collected for the entire study period. Locality level incidence data will be collected over the entire study period.

9.2 Follow-up blood survey at 6-9 months

About 6-9 months after the intervention, all index cases, secondary cases, and two controls for every case will be targeted for blood collection by 250uL microtainer as well as a DBS. Samples will be labeled with a barcode and the date of sample collection. Controls must report no known history of malaria within the last year and will be matched to cases by age, gender, and geography. Study staff will return for up to 2 additional visits to ensure high capture. These samples will be used to study antibody kinetics and refine our current serologic panel of markers of recent versus past exposure in low endemic settings. This serological panel will be used in the end-line survey at the end of the study, expected mid 2017, to measure

seroprevalence. More broadly, this information will help inform future tools used in Swaziland to measure exposure and document interruption of transmission.

9.3 End-line survey (at the end of the study, expected mid 2017)

Towards the end of the study, all residents of Target Areas will be requested to participate in blood collection by DBS. Subjects who did not participate in the intervention are eligible for participation as the goal of the study is to evaluate the impact of the intervention on the community level. In addition to blood collection, we will ask a few short questions about malaria exposure since the intervention. The same barcode will be used to label the blood sample, linking the sample to the same participant. The date of collection will also be used to label the blood sample to differentiate this blood sample from previously collected blood samples (Appendices H & I). Study staff will return for up to 1 additional visit to ensure high capture.

The main purpose of the end-line survey is to perform serology. A serological assessment looking at markers of recent exposure will enable comparisons of recent transmission (and thus impact of RACD vs. TPE) between the two arms. A serological assessment looking at markers of past exposure will enable comparisons of baseline exposure between the two arms. We will also use this measure to look at antibody kinetics (in relation to the baseline and 6-9 month capture points). These samples will also be used to measure infection prevalence.

While the total sample size for the study is expected to be 6000 based on RACD data, we anticipate that 10% of these encounters will occur in individuals that will have received the intervention twice (repeat Target Area enrolled more than 5 weeks since the prior RACD intervention, or more than 8 weeks since the last TPE intervention). These individuals only need to be sampled once. Therefore, we expect to screen about 5400 individuals. While some may not be present to participate in the end-line survey, we expect to also recruit new individuals who were not previously present at the time of the intervention. This sample size will enable us to detect a difference of 3% seroprevalence in the TPE versus 0.6% in the RACD arm (Table 8).

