Finally, cluster randomized controlled trials are the gold standard to compare health services and policy interventions, but significant inputs in time and resources are usually required rendering this study design impractical in program settings. However, as we propose in this project, when many cases are easily available (index cases reported through passive surveillance), existing infrastructure is in place (the current

surveillance team), and the outcome measures can be feasibly measured (incidence will be collected through routine case reporting data, with secondary outcomes measures mainly collected through minimal follow-up visits), a cluster randomized controlled trial can be performed quickly and efficiently.

3 Study aims

The **overall objective** of this proposal is to critically evaluate TPE vs. RACD as a surveillance and response strategy for malaria elimination.

Our **primary aim** is to:

Compare the impact of TPE versus RACD on incidence of malaria cases. We will test the hypothesis that TPE compared to RACD will result in a lower cumulative incidence.

In addition, the following **secondary aims** will be addressed:

Effectiveness:

1. To compare the impact of TPE versus RACD on seroprevalence. We will test the hypothesis that TPE, compared to RACD, will result in lower exposure to malaria, as assessed by antibodies to antigenic markers of recent exposure near the end of the study period (expected mid 2017).
2. To compare the impact of TPE versus RACD on prevalence of infection. We will test the hypothesis that TPE, compared to RACD, will be more effective in decreasing the prevalence of infection near the end of the study period (expected mid 2017).
3. To compare the impact of TPE versus RACD on the proportion of imported incident cases. We will test the hypothesis that TPE compared to RACD will result in a higher proportion of imported incident cases.
4. To compare the impact of TPE versus RACD on time to first incident local case subsequent to the intervention. We will test the hypothesis that TPE compared to RACD will result in a longer time to the first incident local case.
5. To compare the impact of TPE versus RACD on transmission potential, measured by relatedness of strains by microsatellite genotyping. We will test the hypothesis strains detected in TPE versus RACD are less related to ancestor infections.

Feasibility:

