Our primary study outcome is cumulative incidence of passively detected malaria infections in the overall population of the randomized study area localities. If incidence in the RACD arm remains as it was during the 2012-2015 transmission seasons (during which RACD was the standard of care) then given the above assumptions, we would expect cumulative incidence in the RACD arm to be 0.4% or approximately 4 per 1000 persons. If this is the case, our study would have 80% power to detect a reduction in cumulative incidence to 0.2% or 2 per 1000 persons if at least 51 of the 77 study localities had at least one index case (Table 7). Should cumulative incidence in the RACD arm rise to 0.5%, the reduction to 0.25 or 2.5 per 1000 persons in the TPE arm would be detectable with at least 47 localities with at least one case. Should cumulative incidence in the RACD arm fall to 0.3%, reduction to 0.15% or 1.5 per 1000 persons in the TPE arm would be detectable with 57 localities with at least one case. Because of the clustered nature of the data and the variability in cluster size, we used the harmonic mean of the population size (656 per locality, or 41328 total population using the harmonic mean of locality population).

Secondary outcome of effectiveness – Seroprevalence:

In the end-line survey near the end of the study (expected mid 2017), non-index cases residing in Target Areas will undergo blood testing to measure seroprevalence. Index cases will also be included as long as they were not the first index case for a Target Area. The first index case will not be included as this person's malaria exposure was known to occur pre-intervention. The sample size for the seroprevalence measure is expected to be 5400. Based on preliminary data, we expect seroprevalence to be approximately 3% prior to any intervention.[6]

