End-line seroprevalence for RACD was calculated based on an estimate that only 20% of individuals with infection will be detected by RACD and treated, leading to a 20% effectiveness of RACD, or a drop from 3.0% pre-intervention to 2.4% end-line seroprevalence. We believe that TPE will be more effective than RACD in reducing seroprevalence near the end of the study (expected mid 2017). Because of the clustered nature of the data and the variability in cluster size, we used the harmonic mean number of observations expected per locality (60) to generate the effective sample size for analytic power (3780). Using these assumptions, our study would have 80% power to detect a decrease in seroprevalence to 1.18% in the TPE arm if 63 of the 77 localities had at least one case (Table 8).

Secondary outcome on feasibility – Coverage:

For the feasibility outcome measure on coverage, estimates were based on the goal TPE coverage of 80%. This goal is based on modeling data which suggests at least 80% coverage is needed for MDA to be successful, as well as experience from some settings that have successfully interrupted transmission in the setting of MDA [8, 18]. If estimates of incidence in the TPE arm are accurate, approximately 66 index cases will be identified and 1782 individuals will be treated in the TPE-assigned Target Areas. If the true coverage is 80% coverage, we would have a 95% confidence interval between 77% and 83% with this sample size [38].

Secondary outcome on feasibility – Adherence:

To measure adherence to DP, we will perform a pill count in individuals residing in the first Target Area for each TPE locality each transmission season. We will have 5% absolute precision to detect 80% adherence when the sample size reaches 532. If adherence is lower than expected, we will still have 10% absolute precision to detect 50% adherence when the sample size 208.

Table 7. Detectable Reductions in cumulative incidence given different assumptions about Incidence in the RACD

# Total localities with at least one index case	# localities per arm	Number assessed per locality (n)		Cumulative Incidence		Km (coeff of variation)	Z beta	Power
		RACD	TPE	RACD (π_0)	TPE(π_1)			
47.0	23.5	656	656	0.500%	0.250%	0.9	0.84	80%
50.6	25.3	656	656	0.400%	0.200%	0.9	0.84	80%
56.6	28.3	656	656	0.300%	0.150%	0.9	0.84	80%
61.4	30.7	656	656	0.250%	0.125%	0.9	0.84	80%
68.5	34.3	656	656	0.200%	0.100%	0.9	0.84	80%
80.5	40.2	656	656	0.150%	0.075%	0.9	0.84	80%

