Based on equation 4 from Hayes and Bennett International Journal of Epidemiology 1999;28:319-32

Assumes that population is only those in the EAs that have at least one case.

Sample size calculation based on harmonic mean of population size.

Table 8. Detectable reductions in seroprevalence given varying assumptions about prevalence in the RACD arm

# Total localities with at least one index case	# localities per arm	Number assessed per locality (n)		Outcome proportion		Km (coeff of variation)	Z beta	Power
		RACD	TPE	RACD (π_0)	TPE (π_1)			
46.6	23.3	60	60	3.00%	1.35%	0.9	0.84	80%
62.3	31.2	60	60	2.40%	1.18%	0.9	0.84	80%
49.3	24.7	60	60	2.00%	0.83%	0.9	0.84	80%
50.8	25.4	60	60	1.50%	0.57%	0.9	0.84	80%

Based on equation 4 from Hayes and Bennett International Journal of Epidemiology 1999; 28:319-326

Assumes we are including only persons in the target areas in the denominator but evaluating at locality level

Assumes 3 per 100 is the background seroprevalence

Table 9. Sample sizes for primary and secondary aims.

Outcome	Result*	Actual sample size (Effective sample size, based on harmonic mean in clusters)
Primary aim		
Incidence	0.4% (RACD) vs. 0.2% (TPE)	55,928 (41,328)
Secondary aims (effectiveness)		
Exposure (seroprevalence)	2.4% (RACD) vs. 1.18% (TPE)	5400 not including index cases (3720)
Infection prevalence	n/a	5600 includes index cases
Time to first post-intervention incident case	n/a	55,928 (41,328)

Outcome	Result*	Actual sample size (Effective sample size, based on harmonic mean in clusters)
Proportion of imported incident cases	n/a	55,928 (41,328)
Transmission potential	n/a	Genotyping estimated to be performed in 800 index cases** and 35 infections from follow-up cross sectional survey
Secondary aims (feasibility)		
Coverage in TPE Arm	80% (95% CI: 77%-83%)	1782
Adherence in TPE Arm	80%	532
Prevalence of SAEs related to treatment	n/a	5400 not including index cases (3720)
Acceptability	n/a	5400 not including index cases (3720)
Cost	n/a	10 Target Areas/arm

*for some secondary outcomes, power calculations were not performed however effective sample size is shown.

** 200 index cases will be from the study area but an estimated 600 DBS that are already collected as standard surveillance from other parts of the country will also be used to characterize the background genotypes/transmission potential in Swaziland, as it relates to the transmission potential in the study areas.

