Subgroup analyses: Although there is limited power with our constrained sample size, we will describe summary measures of incidence and intervention effects for some specific subgroups of interest within our study area population. Of particular interest are those who did or did not have insecticide spraying of their household areas, strata of risk as determined by the National Malaria Control Program, and season of index case presentation.

Secondary analyses:

Assessments of secondary outcomes will also be conducted using GEE techniques to account for the clustered nature of the data collection as described above. Secondary analyses for prevalence and seroprevalence are restricted to individuals in the Target Areas who will be participating in blood testing surveys conducted towards the end of the study (expected mid 2017). As noted, for analyses of outcomes in the Target Area sample, clustering by both locality and index case area will be accounted for in the modeling approach. To account for possible contamination by proximity to another index assigned to the TPE arm, models will also include adjustment for distance to the nearest index case treated with TPE. Planned secondary analyses and hypotheses are as follows:

Hypotheses regarding the effectiveness of TPE compared to RACD:

1. Comparison of seroprevalence using antibodies to markers of recent exposure. Using the samples collected in the end-line survey near the end of the study (expected mid 2017), we expect that seroprevalence will be lower in the Target Areas receiving TPE than in those receiving RACD.
2. Comparison of prevalence of malaria infection. Using the samples collected in the end-line survey near the end of the study (expected mid 2017), we expect prevalence to be lower in the Target Areas receiving TPE than in those receiving RACD.
3. Comparison of proportion of incident cases that are imported. We expect that local transmission will be reduced by TPE and thus the proportion of subsequent cases imported will be higher in the TPE arm than in the RACD arm. This outcome will be summarized at the locality level and analyzed with locality as the unit of analysis.

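### Section 9.3 states the detectable seroprevalence difference with the arms reversed and cites Table 8 for a pair (3% and 0.6%) that the table does not contain

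*Combined protocol and SAP*

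**What the plan says.** Section 9.3 (End-line survey) closes its sample-size paragraph by saying that about 5,400 people will allow the study to "detect a difference of 3% seroprevalence in the TPE versus 0.6% in the RACD arm (Table 8".

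The other statements on seroprevalence are these:

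- Section 3, first effectiveness aim: the hypothesis is that "TPE, compared to RACD, will result in lower exposure to malaria, as assessed by antibodies to antigenic markers of recent exposure".
- Section 14.3: "we expect seroprevalence to be approximately 3% prior to any intervention". RACD is then assumed to be 20% effective, which gives "a drop from 3.0% pre-intervention to 2.4% end-line seroprevalence".
- Section 14.3, power: "80% power to detect a decrease in seroprevalence to 1.18% in the TPE arm if 63 of the 77 localities had at least one case".
- The RACD/TPE pairs listed in Table 8 are 3.00/1.35, 2.40/1.18, 2.00/0.83 and 1.50/0.57 (all %).
- Table 9: 2.4% for RACD against 1.18% for TPE.
- Section 14.4: "we expect that seroprevalence will be lower in the Target Areas receiving TPE than in those receiving RACD".

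**The concern.** Section 9.3 gives TPE the higher seroprevalence, five times that of RACD. Everywhere else that seroprevalence is planned, TPE is the lower arm. The cross-reference does not rescue the sentence, because swapping the arm labels still leaves a pair that Table 8 does not list. After swapping, 3% against 0.6% would be an 80% reduction (1 − 0.6/3.0). The planning pair is a 51% reduction (1 − 1.18/2.4 = 0.508).

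Section 9.3 calls serology the main purpose of the survey. Someone who reads only that section would take away the wrong direction and a detectable gap about twice the planned one (2.4 points against 1.22).

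**Working it through.** **Inputs.** People assessed per locality n = 60, coefficient of variation k = 0.9 and z for power 0.84 (Table 8); alpha 0.05 (Section 14.4). Sidedness is not stated, so I assume two-sided, z = 1.96. This reproduces Table 8, whereas a one-sided test gives about 49 for the 2.4/1.18 row.

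**Formula.** c = 1 + (1.96 + 0.84)² × V / (p0 − p1)², where V = p0(1−p0)/n + p1(1−p1)/n + k²(p0² + p1²).

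**Reproducing Table 8.**

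| RACD / TPE | c computed | Table 8, total | Table 8, per arm |
|---|---|---|---|
| 3.00% / 1.35% | 46.60 | 46.6 | 23.3 |
| 2.40% / 1.18% | 62.32 | 62.3 | 31.2 |
| 2.00% / 0.83% | 49.32 | 49.3 | 24.7 |
| 1.50% / 0.57% | 50.79 | 50.8 | 25.4 |

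For the planning row, V = 0.0003904 + 0.0001943 + 0.0005793 = 0.0011641 and (0.0122)² = 0.00014884. So c = 1 + 7.84 × 7.821 = 62.3.

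**The Section 9.3 pair.** For 3% and 0.6%, V = 0.000485 + 0.0000994 + 0.0007582 = 0.0013426 and (0.024)² = 0.000576. So c = 1 + 7.84 × 2.331 = 19.3. This matches no row of Table 8. Nor is the pair the 80%-power limit for this sample. Starting from 3%, the formula puts that limit at about 1.55% if c = 63, or about 1.05% if c = 31.5.

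**Could the figures be drops rather than levels?** A 0.6-point fall for RACD would fit Section 14.3 (3.0% to 2.4%). A 3-point fall for TPE would mean 0%, whereas 3.0% to 1.18% is 1.82 points. The sentence also speaks of seroprevalence, not of a change in it.

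**What c counts.** V is the variance contributed by one locality from each arm, so the difference between two arm means with c localities each has variance V/c. The result is therefore a per-arm number. Table 8 prints it as the total and halves it for the per-arm column.

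Power with 63 localities in total (31.5 per arm):

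- 2.4% against 1.18%: √(30.5 / 7.821) − 1.96 = 1.975 − 1.96 = 0.015, or about 51%.
- 3% against 0.6%: √(30.5 / 2.331) − 1.96 = 3.617 − 1.96 = 1.657, or about 95%.
- Starting from 2.4%, setting c = 31.5 gives a TPE value of about 0.77% for 80% power.

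A simulation (20,000 runs, gamma-distributed locality risks with k = 0.9, 60 people per locality, t-test on locality proportions) gave 51% power for 2.4% against 1.18% at 31 localities per arm and 83% at 62 per arm. This confirms the per-arm reading.

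**The case against.** The best defence is that little depends on the sentence. The outcome is secondary, and the aims, Section 14.3, Tables 8 and 9 and Section 14.4 all carry the right direction. The formula is symmetric in the two proportions, so swapping the labels does not change the computed power. As a bare statement of capability, 3% against 0.6% is not an overclaim: the formula gives about 95% power with 31.5 localities per arm. All of this stands, and it keeps the point minor.

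Two stronger readings are tempting, and the documents support neither.

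- A reader might infer that this sentence justifies the size of the survey. It does not. Section 14.1 derives 5,400 from 200 index cases × 30 people = 6,000, less 10% repeats. Section 14.3 says the sample was driven by the number of localities and expected index cases. The sentence only reports what that sample can detect.
- A reader might infer that neither value is in Table 8. In fact 3.00% is there, as a RACD value. The value 0.6% and the pair are what is missing.

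The defence does not explain the reversed arms or the failed citation, and I found nothing else in the documents that does.

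**Conclusion.** The sentence is wrong as written: a minor internal inconsistency in the stated detectable effect for a secondary outcome. The direction contradicts the hypothesis, and the cited table does not contain the pair in either order. The hypotheses, survey size and analysis are unaffected.

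The figures 19.3 and 62.3 should not be read as total localities needed. Both are per-arm results, so the totals would be about 39 and 125. This is why Section 14.3 cannot simply be copied into Section 9.3. The power figures rest on 63 localities split evenly, n = 60, k = 0.9 and a two-sided 5% test; the last is an assumption.

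**What to change.** Replace the Section 9.3 sentence with the Section 14.3 comparison in the right direction: RACD 2.4%, TPE lower. State the power for the planned 63 localities, not for the number observed at study end, which would be post-hoc power.

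Before quoting 80% against 1.18%, check whether Table 8's total column is meant as per arm. If it is, the replacement should give either about 51% power for 2.4% against 1.18%, or about 0.77% as the TPE value detectable with 80% power. Section 14.3 and Tables 8 and 9 should then be brought into line.

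The change in Section 9.3 costs one sentence and alters no procedure. The expected end-line infection prevalences in the genotyping item of Section 14.4 (1.6% TPE, 0.4% RACD) also put TPE higher and are worth checking at the same time.
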